**Specific Aim 1.** Conduct a cluster-randomized trial that includes 36 primary care clinics (34 randomized clinic units, with 3 clinics randomized together due to shared providers) with approximately 300 PCPs and more than 153,000 patients to one of three study arms: (a) PCP-Focused Group: PCP intervention using an EHR-linked, Web-based CP-CDS system, (b) shared decision-making tools (SDMT) Focused Group: PCP intervention using an EHR-linked, Web-based CP-CDS system including additional, or (c) usual care (UC) to assess whether this intervention can improve the delivery of evidence-based, personalized primary and secondary cancer preventive care in rural primary care settings. Specifically, the PCP-focused group will receive a point of care CP-CDS tool that is integrated into the EHR. The CP-CDS provides evidenced-based recommendations to the provider and patient related to overdue cancer prevention screening services and eligible for smoking cessation and obesity management referrals. The SDMT-focused group will also receive the CP-CDS. Furthermore, the SDMT-focused arm provides SDMT to the patient and provider at the time of the visit. The UC arm will not receive the CP-CDS or SDMT but will receive usual best practice advisory suggestions for cancer prevention screening and other usual care.

**Hypothesis 1 (H1).** Eligible study subjects will have significantly different rates of appropriate screening tests for breast, colorectal, and cervical cancer as defined by the U.S. Preventive Services Task Force (USPSTF) during the 12 months after the index visit by study arm, with PCP-focused group higher than UC and SDMT-focused group higher than UC.

**Hypothesis 2 (H2).** Eligible study subjects will have significantly different rates of human papilloma virus (HPV) vaccination in appropriate cases, as defined by the Advisory Committee on Immunization Practices/Centers for Disease Control and Prevention during the 12 months after the index visit by study arm, with PCP-focused group higher than UC and SDMT-focused group higher than UC.

**Specific Aim 2.** Assess the cost of the CP-CDS intervention from the health system perspective through measurement of healthcare utilization and use of diagnostic codes and billing levels related to cancer prevention services.

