**3.3 Study Design:** Supported by CFIR and RE-AIM frameworks, the implementation process for CP-CDS has four phases: a) initial organizational engagement; b) adopting and piloting the CP-CDS with Essentia Health (EH) PCPs and patients; c) a cluster-randomized controlled trial with 3 arms in 36 EH primary care clinics (34 randomized clinic units), and d) evaluation of the implementation process and outcomes. Because three small clinics were randomized together, there are 34 randomized units in this study. Five randomization schemes were developed using random numbers and 1:1:1 allocation to the three study arms. The randomization scheme selected was pre-determined to be the first of five schemes (blind to clinic allocation) with adequate balance on factors of clinic urbanicity, % of patients who were current smokers, % of patients under 30, total number of patient visits per clinic, % of patients with Medicaid, breast cancer screening rate, geographic region, count of patient with serious mental illness, count of patient with pre-diabetes, colorectal cancer screening rate, access to low-dose lung screening, and participation in a community wellness initiative. Quantification of study arm balance was not based on a priori cut-offs but on subjective assessment of balance by the study team.

The two arms were randomly assigned to either the PCP-focused intervention (CP-CDS) or SDMT-focused intervention (CP-CDS + SDMT). The 12-usual care (UC) clinics for the Cardiovascular Wizard studies will continue as control clinics with the CP-CDS (Figure 1) in a 1:1:1 allocation. Because three small clinics were randomized together, there are 34 randomized units in this study.

[figure not shown]
Eligible patients will be allocated to the study arm assigned to their clinic at their index visit.

**3.4 Study Sites:** This study will be conducted at 36 Essentia Health (EH) primary care clinics in North Dakota, Minnesota, and Wisconsin. Leaders at EH are fully committed to the project, as indicated in letters of support from Drs. [name] and [name]. These 36 clinics have used the EpiCare® EHR since 2004 and have, on average, 12 PCPs and 3,996 eligible patients per clinic (range, 318–11,823). Ten participating EH clinics are classified as rural, 7 as micro, 8 as small towns, and 9 as urban by the RUCA2-UR coding system.

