**Study Participants: PCPs and Patients:** To participate, PCPs must practice at one of the randomly assigned EH clinics and be a general internist, family physician, pediatrician, or adult or pediatric care nurse practitioner or physician assistant. There are currently 398 eligible PCPs at the 36 clinics.

To be included in Aim 1 analysis, patients must meet all the following eligibility criteria: (a) be 9–75 years

Figure 1. Research Design for Cluster-Randomized Trial

†PCP= Family Medicine, Pediatrics, General Internal Medicine physicians and adult and pediatric Nurse Practitioners and Physician Assistants

old, inclusive, at an index clinical encounter with their PCP during the accrual period, (b) are not pregnant, not in hospice care, and have no cognitive impairment (e.g., Alzheimer's) diagnosis codes in the last 3 years. For each eligible patient, the study period begins on the date of the first qualifying visit (index visit) at which a cancer screening (or HPV vaccination) is due over the 7.5 months of study accrual (Aug 1, 2018 – March 16, 2019). To extract Wizard CDS-related clinical data at the end of eligible patient's study period, the Wizard may be re-run manually outside a visit at 12 months following the index date. To complete the re-run, HealthPartners will send Essentia Wizard web service IDs for Essentia staff to determine patient IDs and manually fire the Wizard via Epic. Data is then extracted and stored per usual secure Wizard data flow. Based on preliminary EH data in Table 1, we estimate that 152,800 patients will meet eligibility criteria. Less than 5% of patients per year switch from their EH primary care clinic to another EH or non-EH clinic, and losses due to death will be <1% per year. Validated algorithms accurately match over 98% of patients to a regular PCP. Ultimately, after accounting for all exclusions, we anticipate that about 525 eligible adults per PCP (149,625 total patients) will be available for analysis. Plans for dealing with missing data are detailed in Section 2.2.8.5. We previously requested and received a waiver of informed consent for patients from the Institutional Review Board (IRB) because the care recommendations in the CP-CDS intervention are limited to evidence-based care already recommended in current national and regional clinical guidelines. The IRB has waived patient consent in similar circumstances.

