Purpose	
Obtain clarity data for patients in the denominators for H1, H2, Lung, Smoking
 
 
-Descriptive data elements not available in wizard (e.g., insurance status)
 
-Endpoints not available in wizard (e.g., referral to smoking cessation)
 
 
Obtain provider variables for description and secondary analysis
 
 
-Examples: provider type, dept, age, gender
 
 
Obtain RUCA codes for the 36 clinics in study
 
 
-Develop a lookup table or tie location from each encounter to a RUCA code
 
 
[name] cost aims
 
 
-See “Cost” tabs in data dictionary for this aim
 
 
Secondary (if resources): HPV vaccination analysis
 
 
-Identify sample
 
-Identify index visit date, clinic
 
-Gather patient description (e.g., gender)
 
-HPV vaccination dates prior to index date
 
-HPV vaccination dates in year after index date
 

Samples	
1) H1 / H2 / Lung / Smoking sample: patients eligible for any of these denominators because they are due for cancer screening, HPV vaccination, or smoking interventions over the 7.5 mo sample accrual period: Aug 1 2018 – March 16 2019. Will later do 15 mo accrual period of index dates of 8/1/18 – 10/31/19
 
 
-38053 wizard service calls (WSC) “Index 7_5 mo stacked”
 
-Contains study_id, patient_id, Index_VisitDt, visit_provider, visit_location, flags for subsample eligibility (H1 / H2 / Lung)
 
-The smoking sample will be a subset of the H1 / H2 / lung denominator. No separate pulls are needed for such patients.
 
-Some patients show up in the file more than once if they are eligible for more than one subsample denominator. Such patients are included in the file multiple times because they sometimes have different index visit dates and visit_provider, and they are analyzed separately.
 
 
1) [name] cost analysis denominator
 
 
-38053 WSC “Index 7_5 mo stacked” covering the 7.5 month index date period
 
-For the analysis this file will be limited on our end to just the first WSC per patient
 
 
2) HPV sample: patients age 9-17 due for HPV vaccination

Time frame

- Some variables are the status as of the patient index date

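### The 152,800 eligible and 149,625 analysable patients cannot be counts of patients overdue at an index visit; the plan's own counts of that group are about 1.8 to 4 times smaller

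*Combined protocol and SAP*

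**What the plan says.** The Study Participants paragraph under section 3.4 states: "Based on preliminary EH data in Table 1, we estimate that 152,800 patients will meet eligibility criteria". It continues: "we anticipate that about 525 eligible adults per PCP (149,625 total patients) will be available for analysis". Specific Aim 1 gives the trial "more than 153,000 patients", and section 1.3 attaches the same figure to primary care patients. Section 3.4 reports an average of "3,996 eligible patients per clinic".

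The same Study Participants paragraph begins each patient's study period at the "first qualifying visit (index visit) at which a cancer screening (or HPV vaccination) is due over the 7.5 months of study accrual", from 1 August 2018 to 16 March 2019. Section 4.9.2 makes the link explicit for both H1 and H2: patients who are not up to date are the ones who are study eligible.

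Figure A.3 in Appendix A describes the H1/H2/lung/smoking extract for those same dates as "38053 wizard service calls (WSC" and notes: "Some patients show up in the file more than once if they are eligible for more than one subsample denominator". Ages 9-17 form a separate HPV sample with no count given. A later extract with 15 months of index dates is also foreseen.

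**The concern.** The index visit requires that something be due, within 7.5 months. Table 1, the stated source of 152,800, has no such restriction. It covers patients with at least two primary care visits in 36 months and includes those already up to date: 67.1% for colorectal, 65.9% for breast and 53.9% for cervical screening. A count on that basis describes a larger population than the one to be analysed.

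Reach is one of the RE-AIM measures (section 4.7 and Figure A.2), and the 38,053-record file is also the starting point for the cost analysis. A reader who sees a final sample near 38,000 cannot tell whether the plan was fulfilled or fell short by about 75% (1 - 38,053/152,800 = 0.751).

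**Working it through.** No derivation of 152,800 is shown, so it cannot be reproduced. It can be compared with every count of overdue patients that the document gives.

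**1. The stated figures against each other.** 525 × 285 = 149,625, so the analysable figure implies 285 PCPs, a number not in the text. Section 3.4 gives 3,996 × 36 clinics = 143,856 eligible patients. That is fewer than the 149,625 said to remain after exclusions.

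**2. Overdue needs from Table 1 as printed,** N × (1 - proportion up to date). The 12% pooled HPV completion rate is from section 4.9.2.

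- Colorectal: 87,019 × 0.329 = 28,629
- Breast: 44,542 × 0.341 = 15,189
- Cervix: 75,420 × 0.461 = 34,769
- HPV: 40,297 × 0.88 = 35,461
- Sum: 114,048 (118,884 if nobody had completed HPV vaccination)

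This counts a person once per need, over 36 months, and is still below 152,800.

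**3. Overdue patients in section 4.9.2,** over 18 months and for 75% of providers.

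- H1: 9,390 men + 33,264 women = 42,654
- H2: 21,277
- Sum, ignoring overlap: 63,931
- Scaled to all providers: 63,931 / 0.75 = 85,241

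**4. Figure A.3,** same dates as the Study Participants paragraph: 38,053 records, hence fewer distinct patients. Ages 9-17 are not included.

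**5. Ratios.**

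| Comparator | Count | 152,800 / count | 149,625 / count |
|---|---|---|---|
| Table 1 overdue needs, 36 months | 114,048 | 1.34 | 1.31 |
| H1 + H2, all providers, 18 months | 85,241 | 1.79 | 1.76 |
| H1 + H2, 75% of providers, 18 months | 63,931 | 2.39 | 2.34 |
| H1 only, 75% of providers, 18 months | 42,654 | 3.58 | 3.51 |
| Figure A.3 records, 7.5 months | 38,053 | 4.02 | 3.93 |

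The first row counts needs over 36 months, not patients, so it is a bound and not an estimate. The other rows give the range of about 1.8 to 4.

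**6. Sensitivity to what Figure A.3 leaves out.** Suppose the 9-17 sample holds anywhere from 0 to 21,277 patients (an assumption; no count is given). The ratio for 152,800 then runs from 4.0 down to 152,800 / 59,330 = 2.6. If 15 months doubled the file to 76,106 (also an assumption, and generous, because accrual by first visit should slow), the ratio would be 2.0 before ages 9-17 are added.

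**7. Power.** Effective size per arm = n / (1 + (m - 1) × ICC), with 10 clinics per arm and m = n/10.

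- H1, n = 3,133 + 11,088 = 14,221: 1,754 at ICC 0.005 and 483 at ICC 0.02 (stated 1754 and 484)
- H2, n = 7,092: 1,562 and 468 (stated 1562 and 468)

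The sizing therefore reproduces from the overdue counts, not from 152,800. With 38,053/3 per arm for H1, the effective sizes become 1,729 and 481. The detectable rate against 11% is 14.2%-17.3%, compared with 14.1%-17.3% at the planned counts (before any R-square adjustment).

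**The case against.** The strongest defence has four parts.

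- **Eligibility wording.** The lettered criteria cover age, an index encounter, pregnancy, hospice care and cognitive impairment. They do not list being overdue, so 152,800 might be read as a count under those criteria alone. This stands only as an ambiguity: the encounter in criterion (a) is an index encounter, the next sentence defines the index visit by something being due, and section 4.9.2 equates not being up to date with eligibility.
- **Table 1 is incomplete.** It omits patients with missing data, says the full population is larger, leaves out lung screening, starts HPV at age 11 and requires two visits. This stands: 114,048 limits what Table 1 supports as printed, not the true number of overdue needs. Against that, Table 1 is the stated source, spans 36 months and takes breast screening from age 38.
- **The comparators differ in window and scope.** This also stands. A reader might infer a flat fourfold overstatement, but that uses only the Figure A.3 records, without ages 9-17 and before the 15-month extract. A range is all the document supports.
- **A forecast that differs from a later extract is not an error in itself.** True, but the prospective sizing counts in section 4.9.2 conflict with 152,800 as well.

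Three stronger readings are tempting and not supported. That 152,800 is a count of everyone in the age ranges is plausible: the non-overlapping colorectal and HPV rows total 127,316, and all four rows total 247,278. It remains an inference, because no derivation is given. That precision or power is overstated is contradicted by step 7. That the PCP counts contradict one another does not follow: 398 eligible PCPs × 75% participation = 298.5, which matches the approximately 300 stated elsewhere, and 300 × 0.95 would give the implied 285 (the 95% is a guess).

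**Conclusion.** The point holds as an unreconciled and misleading enrolment figure. Neither 152,800 nor 149,625 can be the number of patients overdue at an index visit in the 7.5-month window. They exceed the plan's own counts of overdue patients or records by about 1.8 to 4 times, and they exceed even the double-counted overdue needs in Table 1 as printed. The per-clinic average does not fit either.

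The conclusion rests on reading eligibility as the index-visit definition and section 4.9.2 do, and on Table 1's printed figures. The exact factor cannot be fixed, because the overlap between endpoints, the number of distinct patients behind the 38,053 records and the size of the 9-17 sample are not given. The power calculation is not affected.

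**What to change.** In Specific Aim 1, section 1.3, section 3.4 and the Study Participants paragraph, describe about 153,000 as the source primary-care population and state how it was derived and over what window. Do not present it as the number meeting eligibility or available for analysis. Reconcile the 3,996 per clinic with it.

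Give the expected number of distinct overdue patients separately for H1, H2 in adults, HPV at ages 9-17 and lung screening. Do this for the 7.5-month window, and for the 15-month window if it will be used, and reconcile the numbers with section 4.9.2 and Figure A.3. Keep planned numbers and extracted counts labelled as such. The PCP counts need no merging; at most, label which are eligible and which are participating.

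The cost is a text correction and a de-duplicated count from files already specified. The stated number of patients becomes smaller; no design, model or test changes.

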### **3.5 Description of Usual Care and Intervention Conditions**

**3.5.1 Usual Care Condition (Arm C):** In the usual care group of the study, clinics and their PCPs will have no access to the CP-CDS intervention. Some existing Epic reminder systems in EH clinics do address cancer screening tests with reminders that are pop-up alerts, which are easily ignored. These alerts are marginally effective, resulting in current suboptimal rates of cancer screening tests and very low rates of referrals for weight management and smoking cessation and HPV vaccinations (Section 3.2). There is no systematic CP-CDS system in EH clinics other than what will be implemented as part of this project in the 2 intervention arms. Simple alerts have generally been ineffective due to many factors, such as alert fatigue, provider burden, and no patient engagement.

**3.5.2 Intervention Condition:** CP-CDS is rooted in a series of antecedent studies that have developed successful forms of outpatient CDS. Our project's intervention will have 2 experimental arms:

**PCP-focused group and SDMT-focused group.** Specific steps in design and implementation of the CP-CDS intervention are described next.

**Step 1. Identify Eligible Patients, Extract Clinical Data from EHR, and Send to Web site:** In HL102144, we created and validated programming to (i) extract pharmacy, laboratory, vital signs, demographic, comorbidity and other data from the EHR, and (ii) export these data to a secure Web site inside the HealthPartners Medical Group firewall. Web site algorithms will use these EHR-extracted data to identify eligible patients needing primary and/or secondary cancer prevention during a routine, non-urgent primary care visit. Patients younger than 18 years will not be identified for smoking cessation or weight management treatment or referrals due to the need for different approaches required by adolescents, which is beyond the study scope. Patients 9 to 17 years old will be identified for HPV vaccination only if a parent is present during the clinical encounter. Patients aged 18 and older will be identified for cancer screening tests, HPV vaccinations, smoking cessation, and weight management, if eligible, according to national guidelines previously presented. To avoid firing the CDS too often and burdening the PCP care team, the CDS algorithms may be suppressed.

**Step 2. Create Primary & Secondary Cancer Prevention CDS Algorithms:** The Web-based treatment algorithms used in this project are based on national guidelines, approved in advance by primary care clinical leaders at EH, and reflect current evidence and community standards of care. Similar algorithms have been tested in 2 previous research projects (DK068314, HL102144). The algorithms for this project will include ICD-10^72 codes and will be updated (and revalidated) as required by changes in national guidelines. The Breast Cancer Risk Assessment Tool (BCRAT, NCI), Colorectal Cancer Risk Assessment tool (CRCRAT, NCI), and the Risk-based National Lung Cancer Screening Trial Outcomes Tool (RNOT) lung cancer risk assessment tool will compute personalized risks for these cancers, which can be presented during the CP-CDS encounter.

**Step 3. Collect Patient-Centered Data Using Personalized Tools:** During their office visit, patients in

need of specific screenings or HPV vaccination will receive patient-centered, personalized tools, developed by the team based on national standards, including: Breast cancer shared decision-making tool, colorectal cancer decision-making tool, and HPV vaccination shared decision-making tools. Patients eligible for lung cancer screening may also receive the lung cancer shared decision-making tool from the CDC Agency for Healthcare Research and Quality (AHRQ) or a tool adapted from the AHRQ tool. Only patients needing a cancer prevention intervention will be presented these tools and questions.

**Step 4: Identify Available Treatment Options for Cancer Prevention Needs:** Web-based algorithms identify evidence-based prevention options that address each unmet cancer prevention need. Specific CDS recommendations given to a patient are based on both (a) statements from USPSTF, NCI, CDC, AHRQ, and ACIP, and (b) the specific patient's current clinical state, including age, sex, smoking status, BMI, HPV vaccine status, comorbid conditions, allergies, and past screening tests for the 3 target cancers. Cancer screening and treatment recommendations for smoking cessation, HPV vaccination, and obesity management are given as needed. The PCP uses the CP-CDS Active Guidelines or "Wizard Guidelines" to refer the patient directly to appropriate internal or community resources for smoking cessation or obesity management and to order HPV vaccinations and appropriate cancer screenings. Active Guidelines are a manually accessed EHR form designed to fit into providers' workflow containing actionable functions such as order sets and referrals.

**Step 5: Present Cancer Prevention Options to PCPs and Patients: Clinic Workflow:** In this project, CP-CDS recommendations are presented to the patient directly and the PCPs using a sequence of clinic staff steps successfully implemented in previous studies and pretested interface formats. Participating PCPs in intervention clinics are trained to use the provider and patient interfaces of CP-CDS as follows: When a patient needing cancer prevention interventions has a clinical encounter with a PCP, the following protocol is automatically implemented: (i) after vital signs are entered into the EHR, CP-CDS assesses cancer prevention needs, identifies target patients, and provides a best practice alert (BPA). In response to a single click, CP-CDS displays the interface screen to the CMA within 1 second (with no additional prompts or triggers needed). The CMA prints the patient and PCP versions of the CP-CDS sheet, (ii) if a patient's mental and physical status appears stable, the CMA hands the patient sheet (example in Appendix B) to the patient, saying "the caution marks show how you can prevent health problems such as cancer, diabetes, stroke, and heart attacks. If you are ready to work on any of these things, please talk with your doctor during your visit today." (iii) for both the PCP-focused and SDMT-focused groups, a printed version of the provider CP-CDS (example in Appendix B) is either placed in the basket outside the exam room for rapid review by the PCP before entering the exam room or displayed on the EHR screen with one click on the EHR navigator bar, depending on the PCP preference, with the SDMT-focused group also receiving any relevant SDMT, and (iv) in both the PCP- and SDMT-focused groups, the PCP uses the CP-CDS PCP interface to guide changes in cancer prevention care and uses the CP-CDS patient interface to reinforce patient actions. The CP-CDS will embrace the 5 A's (Ask, Advise, Assess, Assist, Arrange) to promote patient activation by having these elements embedded in the provider interface. The patient version may be printed as part of the After-Visit Summary. After discussion with the patient, the PCP can order screening tests, medications, or make referrals to internal programs or community resources to address smoking and/or obesity by using the CP-CDS Active Guidelines.

**Provider Interface:** CDS included on the provider interface is specific and based on whether the patient has significant cancer risk factors or is due for a cancer screening. Both PCP- and the SDMT-focused groups use the provider interface. Prototype CDS algorithms are based on the recommendations published by USPSTF, NCI, CDC, and ACIP. They will be updated over time to ensure ongoing congruence with national evidence-based guidelines. Primary and secondary cancer screening information displayed on the CP-CDS provider interface are: smoking and obesity management options, medical interventions (HPV vaccine status, and screening status for breast, colorectal, lung, cervical cancer). All treatment recommendations are labeled as suggestions, and the interface sheets emphasize that this CDS does not take the place of clinical judgment or a PCP's detailed knowledge of a particular patient. The provider interface is a powerful visit-planning tool that most PCPs prefer to view in print just before entering the exam room.

**Patient Interface:** A simple visual approach is preferred, because patients may have low levels of numeracy and misinterpret probabilistic information. A visual display of recommended lifestyle modifications (smoking cessation, weight reduction/counseling), medical interventions (HPV vaccination, medications for tobacco cessation), and screening tests for the 4 target cancers are included, depending

on the needs of the patient identified by the CDS algorithms. Similar visual patient interfaces we used in earlier studies have been well received by most adult and teen patients, accommodate low numeracy, and have been shown in studies by others to be a strong motivational strategy. However, the prototype interfaces shown in the Appendix B will be substantively modified to address key issues related to cancer prevention care, with extensive input from our adult and teen representatives from EH Patient Councils and extensive pilot testing before randomization.

**Four SDMTs:** For patients in need of breast, lung, or colorectal cancer screen or who are not up to date on HPV immunizations, four separate SDMT tools will be available. Each tool will include five components: 1) overview of screening; 2) screening options; 3) benefits of tests; 4) risks; and 5) how do I make a decision?

Breast cancer screening: We created our own tool: a static, printable SDMT for women in need of screening ages 35 to 74.

Colorectal cancer screening: We created our own tool: a static, printable SDMT for men and women in need of screening ages 50 to 75.

HPV vaccination: We created two separate tools: a static, printable SDMT for parents of children in need of HPV ages 9 to 17, and a static, printable SDMT for adults in need of HPV ages 18 to 26.

Lung cancer screening: We will use one of two tools: a tool developed by HealthPartners based on decision aids from the AHRQ: a static, printable SDMT for adults with a 30-year pack habit ages 55 to 80.

**Step 6. PCP Activates CP-Active Guidelines:** The Active Guidelines, or “Wizard Guidelines”, is built into the EHR and provides options for orders and referrals based on the wizard recommendations. The CP-Active Guidelines will contain information on clinic- and community-based resources for smoking cessation and weight management services, counselors, and programs with locations, contact information, program type, and delivery methods.

**Step 7: Iterative Use of Cancer Prevention CDS over Series of Visits:** A key design feature of this intervention is its repeated use at all routine office visits of eligible patients in intervention study arms A & B. Pilot data indicate that nonpregnant eligible adults will average 3-6 primary care visits during the anticipated 33-month accrual and follow-up periods. After the CP-CDS is activated during the accrual period, subsequent activations may be limited to once every 120 days to minimally disrupt clinic workflows. In a previous study (HL102144), rates of use of a cardiovascular CDS system by consented and non-consented PCPs were 70%-80% of targeted care visits. CP-CDS gives updated treatment suggestions for patients and PCPs to consider at each visit, because CDS evolves as the patient's clinical status, lifestyle, and cancer prevention needs change over time.

